# **Study purposes**

"Hygeia Touch Self Sampling Kit for Women" was created and commissioned by Hygeia Touch Inc. This kit includes a self-sampling swab developed for Oriental women. It is constructed of non-toxic and non-allergenic materials and can be used by you. Collect enough exfoliated vaginal cells to test for human papillomavirus. This is a single-use sterilizing product. It is simple to use and allows women to self-collection freely and comfortably. The collected specimens should be forwarded to a reputable laboratory at room temperature for high-risk HPV type testing. We intend to give an alternative for women who do not obtain regular cervical screening, raise the national cervical screening rate, and further lower the incidence of cervical cancer.

The trial will involve 1,200 women who will self-sample using a kit for high-risk HPV testing, and their results will be compared to cervical samples collected by physicians. The physician-collected samples will serve as the standard for evaluating the consistency of HPV typing results between the two methods. This kit is classified as a Class II medical device by the TFDA of the Ministry of Health and Welfare. If the results demonstrate strong consistency between self-sampling and physician testing, an application will be made to classify the kit as a Class 2 medical device for women's self-sampling of high-risk HPV types.

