#### Statistical methods

This study is a multi-center, operator-blinded clinical trial in Taiwan . It mainly explores the consistency of self-sampling of the product and that of doctors . This trial will use the test results of samples collected by doctors as the standard and compare them with the HPV type test results

of self-collected specimens from the same subject to verify the HPV types in the samples collected by doctors and self-sampling. consistency.

A. The trial design uses the status of cervical precancerous lesions as a stratification variable. Five groups of subjects will be recruited according to the following proportions. It is expected to recruit a total of 1,200 subjects:

The 5 groups of subjects included in the study	Inclusion ratio	Estimated number of people to be included
1. Those with no abnormal smears or history of cervical lesions	10%	120 people
2. Those who have had mild smear or pathological tissue abnormalities within 3-12 months and need to undergo cervical smear follow-up	15%	180 people
3. Have had moderate to severe smear or pathological tissue abnormalities or cervical cancer, have undergone cone surgery, and are currently being followed	20 %	240 people
4. Those who have mild smear or pathological tissue abnormalities within 3 months and have not yet been treated	20 %	240 people
5. Those who have found moderate to severe smear or pathological tissue abnormalities or cervical cancer within 3 months and have not yet received treatment	35%	420 people
The total number of subjects expected to be included		1,200 people

Based on clinical research, it is estimated that the HPV positivity rates in the above five groups are (1) 10%, (2) 70%, (3) 50%, (4) 70%, and (5) 90% respectively. Based on the experimental design, under the stratified recruitment ratio, the overall HPV positivity rate is expected to be approximately 67%.

- B. According to the main evaluation indicators of the test, the consistency of this study is defined as:
- 1. HPV16, 18, 31, 33, 35, 39, 45, 51, 52, 56, 58, 59, 66, 68 are cancer-causing high-risk types. The agreement on detecting the presence of high-risk HPV between physician-sampled specimens and self-collected specimens is listed as the main purpose. Consistency is defined as follows:
- (1) The high-risk HPV test results are consistent (agree). The test results indicate that either of the above-mentioned high-risk HPV types is present in both cases or that neither of them has high-risk HPV types.

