### **Secondary evaluation indicators:**

- A. The success rate (proportion of effective specimens) of HPV typing in physician - collected and self- collected specimens of all detectable HPV types.
- B. The incidence of adverse reactions was used as the safety evaluation index to evaluate whether there would be adverse reactions caused by doctors' self-examination of vaginal secretions or self-examination of vaginal secretions. The test process was recorded according to the grading standard of CTCAE version 5.0 .
- C. Evaluate whether women can complete effective self-specimen sampling by following the instructions or videos. The beta-globin of the test results will be used as an evaluation index for valid specimens, and the reliability of the explanatory files will be evaluated by the results of the questionnaire survey.
- D. -collection success rate (proportion of effective specimens) and consistency evaluation of each group under the test group .
- E. The correlation between the HPV test results collected by physicians , the HPV test results of self- collected samples, and the results of Pap smear and histopathological diagnosis at the same time . Taking the most serious pathological diagnosis as the standard, calculate
  1. Predict the sensitivity, specificity, positive predictive value and negative predictive value of cervical lesions based on the HPV test results of the samples taken by doctors
  2. Predict the sensitivity, specificity, positive predictive value and negative predictive value of cervical lesions based on the test results of self- collected samples
- F. The questionnaire was used to evaluate the satisfaction of the subjects' self-testing .

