## Statistical considerations

### Statistical design, methods and analysis procedures

A. This study is a multi-center clinical trial in Taiwan to test the blindness of operators . It mainly explores the consistency between self- testing of products and doctor -testing . In this experiment, the test results of samples collected by doctors will be used as the standard, and compared with the results of HPV type test of samples collected by the same subject to verify the consistency of HPV types in samples collected by doctors and self- sampled samples.

B. The experimental design uses the status of cervical precancerous lesions as a stratification variable, and the 5 groups of test groups are divided into the following proportions:

5 groups of subjects included in the subjects	Inclusion ratio
1. No history of abnormal smear or cervical lesions	10%
2. There have been mild smears or pathological abnormalities within 3-12 months, and those who need to receive Pap smear follow-up	15%
3. Those who have had moderate to severe smear or pathological abnormalities or cervical cancer, have received conical surgery , and are currently receiving follow-up	20 %
4. Mild smears or pathological tissue abnormalities within 3 months, who have not yet been treated	20 %
5. Moderate and severe abnormalities in smear or pathological tissue or cervical cancer found within 3 months, and those who have not received treatment	35%

According to relevant literature research, it is estimated that the positive probability of HPV in the five groups is (1) 10% , (2) 70% , (3) 50%, ( 4 ) 70% , ( 5 ) 90%, depending on the experimental design Under the stratum recruitment ratio , the overall HPV positive rate is expected to be about 67% , as shown in the table below .

Stratification	AI location rate	S stratified HPV positive prob.
1. No history of abnormal smear or cervical lesions	0.1	0.1
2. There have been mild smears or pathological abnormalities within 3-12 months, and those who need to receive Pap smear follow-up	0.15	0.7

3. Those who have had moderate to severe smear or pathological abnormalities or cervical cancer, have received conical surgery , and are currently receiving follow-up	0.20	0.5
4. Mild smears or pathological tissue abnormalities within 3 months, who have not yet been treated	0.20	0.7
5. Moderate and severe abnormalities in smear or pathological tissue or cervical cancer found within 3 months, and those who have not received treatment	0.35	0.9

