Total	0.67	

C. Subjects who meet the admission requirements will be included in one of the 5 stratified groups according to their pathological conditions. All test institutions will accept cases through competition. After the stratified groups reach the predetermined acceptance ratio, no subjects from this group will be recruited.

D. In this experiment, each subject will provide two specimens, one from a doctor's examination and one from a self- examination . In order to maintain the scientific nature of the consistency assessment, the tester will be blinded , that is, the tester cannot know the samples corresponding to the two collection methods of any subject.

E. This study intends to achieve the blindness requirement by means of coding, that is, the sample number collected by the doctor is the number of the subject of this study (the number is given according to the order of admission ), and the self- collected sample of the same subject is based on the sample number collected by the doctor, and the number obtained by random garbled operation makes it impossible to directly correspond to the sample collected by the doctor .

F. According to the main evaluation indicators of the test, the consistency of this study is defined as : for 14 high-risk types such as HPV16, 18, 31, 33, 35, 39, 45, 51, 52, 56, 58, 59, 66, 68, the main purpose is to list the consistency (agreement) of the detection in the doctor's inspection and self- sampling samples . Consistency is defined as follows:

- (1) The high-risk HPV test results are consistent (agree) , and the test results show that both of them have any of the above-mentioned high-risk HPV or neither of them has high-risk HPV ..
- (2) The test results of high-risk HPV are inconsistent ( disagree ). One of the samples collected by doctors and self- collected samples does not have any of the above-mentioned high-risk HPV types , and the other has any of the above-mentioned high-risk types .

According to the definition of the test result, a contingency table can be obtained as follows, the Kappa statistic  $K = (P_0 - P_c) / (1 - P_c)$  for statistical verification, where  $P_0 = (a+d) / (a+b+c+d)$  is the observed agreement (observed agreement), and  $P_c = \left( \frac{cm_1 \times rm_1}{n} \right) + \left( \frac{cm_2 \times rm_2}{n} \right) / n$  is the theoretical expected

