aHPV 16: HPV 16 present only and/or co-infections with other types; bHPV 18: HPV 18 present only and/or co-infections with other types; cHPV 16/18: HPV16 and/or HPV18 present and/ or co-infections with other types; dHPV31, 33, 35, 39, 45, 51, 52, 56, 58, 59, 66, and 68 excluding HPV16 and HPV18 ; eHPV 6, 11, 53, 54, 61, 62, 69, 70, 72, 73, 81, 82 and 84 excluding HPV16, 31, 33, 35, 39, 45, 51, 52, 56, 58, 59, 66, and 68.

Table 8 Distribution of all measurable HPV types in medical samples and self- collected samples of each group

HPV	Total	Group 1	Group 2	Group 3	Group 4	Group 5
	( N=)	( N=)	( N=)	( N=)	( N=)	( N=)
6	Physician	Self	Physician	Self	Physician	Self
11						
16						
18						
31						
33						
35						
39						
45						
51						
52						
53						
54						
56						
58						
59						
61						
62						
66						
68						
69						
70						
72						
73						
81						
82						
84						
Negative						

Figure 2. Distribution of HPV types on physician-collected and self-collected specimens

Figure 3. Distribution of HPV types in Physician-collected and Self-collected specimens without precancerous lesions or cervical cancer (N = )

Figure 4. The distribution of HPV types on physician-collected and self-collected specimens of participants with cervical intraepithelial neoplasia grade 1

Figure 5. The distribution of HPV types on physician-collected and self-collected specimens of participants with cervical intraepithelial neoplasia grade 2 (N = )

Figure 6. The distribution of HPV types on physician-collected and self-collected specimens of participants with cervical intraepithelial neoplasia grade 3 (N = )

Table 9 Sensitivity, specificity, PPV and NPV between medically collected and self- collected HPV test results and cervical histopathology

cervical histopathology	self- collected specimen		Physician check		Relative accuracy	
	n/N	(95% CI)	n/N	(95% CI)	(95% CI)	p value
CIN1+						
Sensitivity						
Specificity						
Positive predictive value						
Negative predictive value						
CIN2+						
Sensitivity						
Specificity						
Positive predictive value						
Negative predictive value						
CIN3+						
Sensitivity						
Specificity						
Positive predictive value						
Negative predictive value						

\*No histological diagnosis is calculated as Negative

Table 10 Analysis of Satisfaction Questionnaires Included in Total Cases (N = , ITT)

satisfaction survey	very low		Low		high		very high	

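### Table 9's pooled PPV, NPV and specificity depend on the quota-fixed case mix as well as on test performance, and do not carry over to women who miss regular screening

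*SAP*

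**What the plan says.** - **Recruitment.** The Protocol (Statistical methods) states: "Five groups of subjects will be recruited according to the following proportions". The shares are 10/15/20/20/35%, or 120/180/240/240/420 of 1,200 women. The SAP (Statistical design, methods and analysis procedures) says "The experimental design uses the status of cervical precancerous lesions as a stratification variable" and closes each stratum when it is full: "After the stratified groups reach the predetermined acceptance ratio, no subjects from this group will be recruited".
- **Planned accuracy analysis.** SAP secondary indicator E plans to "Predict the sensitivity, specificity, positive predictive value and negative predictive value of cervical lesions" separately for physician-collected and self-collected samples, taking the worst pathology as the standard. The output is "Table 9 Sensitivity, specificity, PPV and NPV between medically collected and self- collected HPV test results and cervical histopathology". It has blocks for CIN1+, CIN2+ and CIN3+, columns for each sampling method, and a relative-accuracy column with a p value. It has no rows by group. Its footnote counts women without histology as disease-negative.
- **Stratification elsewhere.** The Protocol's inclusion section calls the five groups the basis for stratified analysis, and Tables 5 and 8 are split by group. Table 9 is not. Neither document gives a re-weighting, a target prevalence, or a note limiting Table 9 to the trial's mix.
- **Intended use.** Protocol, Study purposes: "We intend to give an alternative for women who do not obtain regular cervical screening".
- **Status.** The SAP labels as exploratory everything other than the primary and secondary indicators, so Table 9 is a planned secondary result.

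**The concern.** Predictive values depend on how common disease is among those tested. Here the sampling variable is lesion status, which is closely tied to the outcome that Table 9 predicts, so disease frequency in the pooled sample is largely a design choice. Specificity is affected too: women without CIN2+ come from groups whose expected HPV positivity runs from 10% to 90%, so the pooled false-positive rate is an average over the quota mix.

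Different quotas with the same test behaviour in every group would print different figures. A reader who takes the printed PPV as what a woman outside regular screening can expect after a positive self-sample would probably be far too pessimistic about her result. The pooled NPV would err the other way, understating the reassurance of a negative result.

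**Working it through.** **Inputs from the documents.** Quotas w = 0.10, 0.15, 0.20, 0.20, 0.35. The Protocol's expected "HPV positivity rates in the above five groups are (1) 10%, (2) 70%, (3) 50%, (4) 70%, and (5) 90% respectively" gives p = 0.10, 0.70, 0.50, 0.70, 0.90.

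**Step 1: the plan's own figure.** Σwp = 0.010 + 0.105 + 0.100 + 0.140 + 0.315 = 0.670. The SAP says "overall HPV positive rate is expected to be about 67" percent, so it reproduces.

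**Step 2: who supplies the positives and negatives (no outside assumption).**
- Share of positives, wp/0.67: 1.5, 15.7, 14.9, 20.9, 47.0%.
- Share of negatives, w(1−p)/0.33: 27.3, 13.6, 30.3, 18.2, 10.6%.

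The PPV denominator is almost half Group 5 and almost untouched by Group 1.

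**Step 3: illustration with assumed CIN2+ rates.** The documents give no CIN prevalence. Let D be the assumed CIN2+ rate per group and s = 0.95 the assumed sensitivity in every group. Take p as the positivity of the test result used in Table 9.
- PPV = s·ΣwD / Σwp
- NPV = 1 − (1−s)·ΣwD / Σw(1−p)
- Specificity = [Σw(1−p) − (1−s)·ΣwD] / (1 − ΣwD)

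| Assumed D, Groups 1-5 (%) | ΣwD | Pooled PPV / NPV / spec. | Group 1 PPV / NPV / spec. |
|---|---|---|---|
| 0.5, 3, 5, 8, 40 | 0.1710 | 24.2 / 97.4 / 38.8% | 4.8 / 99.97 / 90.4% |
| 1, 3, 5, 8, 60 | 0.2415 | 34.2 / 96.3 / 41.9% | 9.5 / 99.94 / 90.9% |
| 2, 5, 5, 15, 80 | 0.3295 | 46.7 / 95.0 / 46.8% | 19.0 / 99.89 / 91.7% |

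Middle row in full: PPV = 0.95 × 0.2415/0.67 = 34.2%. NPV = 1 − 0.05 × 0.2415/0.33 = 96.3%. Specificity = (0.33 − 0.0121)/0.7585 = 41.9%. In Group 5 alone the same assumptions give PPV 0.57/0.90 = 63.3%, NPV 0.07/0.10 = 70% and specificity 0.07/0.40 = 17.5%.

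**Step 4: change only the mix.** As a deliberately simple case, let CIN2+ be exactly Group 5 and keep every group's positivity fixed.

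| Mix, Groups 1-5 (%) | PPV | NPV | Specificity |
|---|---|---|---|
| Quotas | 0.315/0.670 = 47.0% | 0.295/0.330 = 89.4% | 45.4% |
| 20 each | 0.18/0.58 = 31.0% | 95.2% | 50.0% |
| 35, 20, 20, 15, 10 | 0.09/0.47 = 19.1% | 98.1% | 57.8% |
| 90, 3, 3, 3, 1 (assumed screening-type mix) | 0.009/0.156 = 5.8% | 99.9% | 85.2% |

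**Step 5: is inserting a new prevalence enough?** No. Putting 1% prevalence into Bayes' rule with the pooled sensitivity 0.90 and specificity 0.454 gives 0.009/(0.009 + 0.546 × 0.99) = 1.6%. The group-level calculation at the same 1% prevalence gave 5.8%. The pooled specificity carries the quota mix with it, so the re-weighting has to start from group results.

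**Step 6: precision in Group 1.** Expected positives are 120 × 0.10 = 12. One CIN2+ case among 12 has an exact 95% interval of 0.2% to 38.5%.

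**The case against.** The strongest reply is that nobody has claimed these values for the screening population. The registration case rests on agreement with the physician sample, tested by kappa against 0.66. Table 9 sets two methods side by side in the same women, and its relative-accuracy column suggests that this comparison is its main purpose. A pooled predictive value is a correct description of the enrolled sample. This stands: the pooled figures are not wrong as trial descriptions, and a reader who infers that they must be deleted goes further than the documents support. But neither document limits the values to the recruitment mix, and the stated purpose points readers to a different population.

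Four further points stand in part.
- **Quotas alone do not set the values.** Within-group test performance matters as well. The same logic reaches specificity, so it would be inconsistent to single out PPV and NPV.
- **Group 1 is not the intended user.** It is defined by no abnormal smear or lesion history, not by screening attendance, and the physician samples are taken in outpatient clinics. It is a rough proxy only.
- **The prevalences are assumed.** The sizes in Steps 3 and 4 are illustrations. The shares in Step 2 need only the documents' figures.
- **Group rows bring their own problem.** Colposcopy is done only if needed, and no histology counts as negative. If Group 1 women are seldom biopsied, which the documents do not say, their printed PPV is pushed towards 0% and their NPV towards 100%. Group rows without histology counts could mislead.

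**Conclusion.** The point holds for absolute PPV, NPV and specificity. These depend on the quota-fixed mix together with within-group performance, and they do not carry over to women outside regular screening. What rests on the documents alone is that Group 5 supplies 47.0% of expected positives and Group 1 supplies 1.5%. Under the assumed CIN2+ rates and 95% sensitivity, pooled PPV is about 24-47% against 5-19% in Group 1, and pooled NPV is about 95-97% against 99.9% or more. In all three scenarios the pooled PPV was higher, and the pooled NPV and specificity lower, than in Group 1.

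A reader might infer that the trial's main conclusion is at risk. The documents do not support that: the primary kappa test does not use histology, and the self-versus-physician comparison is paired within women, so both methods face the same mix. This is a secondary result that should be corrected before the tables are produced.

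**What to change.** - Add rows by group to Table 9 for PPV, NPV and specificity, with exact intervals.
- In each group, print how many women had histology. Give the group-level values both under the current footnote and among women with histology. The second set comes from a selected subset, so the two should be read together.
- Add one estimate re-weighted from the group-level results to a stated screening mix. Print the weights and a range of mixes. Do not re-weight by inserting a new prevalence next to the pooled specificity.
- If pooled values are kept for the paired comparison, label them as applying to the trial's recruitment mix only.

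**Cost.** This is a change to the SAP and one table shell. Group membership and histology are already recorded, so no new data are needed. The price is precision: intervals will be wide, above all in Group 1 with about 12 expected positives, and the re-weighted figure inherits that imprecision because it leans on Group 1. The report should say so.
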